Health
Sydney
Local Health District

PMBC Sleep Program

PROTOCOL NUMBER: VERSION 1.0 (APRIL 2018)

ADMINISTRATIVE INFORMATION

DATA CATEGORY	INFORMATION
Scientific Title	A pilot evaluation of sleep program to improve sleep quality in male psychiatric HDU inpatients
Public Title	PMBC sleep program
Date of Registration	TBC
Primary registry and trial identification number	TBC
Date of Registration in primary registry	TBC
Secondary identification numbers	TBC
Source of monetary or material support	Fully funded by the Sydney Local Health District (\$50,000)
Primary Sponsor	Sydney Local Health District
Contact for public queries	[name] [name], [contact]
Contact for scientific queries	[name] [name], [contact]
Countries of recruitment	Australia
Health condition(s) or problem(s) studied	Inpatient male HDU psychiatric patients of all diagnoses
Intervention(s)	Ward-based initiatives and activity groups
Comparator	Routine male inpatient psychiatric HDU patients' length of stay with and without therapy; previous admissions
Inclusion criteria	Males aged 18+ years. Able to give informed written consent. Literacy in English. Inpatient at PMBC psychiatric Male High Dependency Unit (HDU).
Exclusion criteria	Current substance dependence. Severely unwell such that not able to give consent or tolerating participation in group sessions. Severe cognitive impairment or thought disorder. Not

	proficient in English. Recent transmeridian (>2 time zones) travel (within last 1 month).
Study type	Interventional; Allocation: nonrandomized; Masking: none (open label trial)
Primary Purpose	Pilot Study, Feasibility Study
Date of first enrolment	May 2018
Target sample size	N/A (Pilot study, rolling recruitment)
Recruitment status	Recruitment not yet commenced.
Primary outcomes	Actigraphic changes in sleep duration (Respironics Actigraphy data)
Key secondary outcomes	
Sleep quality (weekly Visual Analogue Scale (VAS) and Pittsburgh Sleep Quality Index measured at start and end of study)
 
Self-report duration
 
Length of stay in HDU
 
Use of as needed (PRN) sedatives for sleep
 
Sleep efficiency (actigraphy)
 
Engagement in group
 
Autonomy
 
Participant satisfaction

Protocol Version:	Version 1.0, April 2018
Revision Chronology	Version 1.0, April 2018: Original.
Protocol Amendment Number	0
Authors	[name] BE(Hons) BCom MBBS, [name] BPsych(Hons), [name] MBBS PhD

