Research has shown that the sleep-wake cycle is strongly linked to the environment (Czeisler et al. 1980; Rea et al. 2008) and disruptions to this cycle may result in sleep disturbances as well as negative cognitive and psychological consequences (Lane & East, 2008). Hospital environments tend to report low lighting levels which may distort the normal circadian sleep-wake rhythms. Bendetti et al. (2001) assessed an inpatient hospital setting over 2 years and reported an average reduction of 3.67 days in admission in those rooms facing east compared to rooms facing the west. The addition of increased outdoor activities and light glasses in the current study increases exposure to light which can assist in stabilising the circadian rhythm.

Moreover, evidence-based interventions such as cognitive behavioural therapy for insomnia (CBT-I) has shown promising results within clinical settings involving patients with schizophrenia, psychosis and patients in acute care (Freeman et al., 2015; Sheaves et al., 2017).

This study has 2 goals. The first goal is a pilot study of an integrated, ward-based behavioural therapy (the Sleep Program) to improve the quality sleep of psychiatric inpatients in order to determine its effect, variance of effect and feasibility. The second is to describe the characteristic of sleep, activity and light exposure of patients in a high dependency psychiatric unit using wrist actigraphy.

Actigraphy

Wrist actigraphy has been used to measure sleep rhythms for over 25 years (Kripke et al., 1978, Mullaney et al., 1980). Actigraphs are watch like devices generally placed on the wrist to record movement. Most are based on weighted activity (accelerometry) counts in a given epoch of time which detect sleep/wake according to threshold values. Activity data is then processed and analysed by computer software programs and specialized algorithms are used to estimate sleep and activity parameters. The analysis utilises algorithms which have been developed, compared and validated since the original use of actigraphs (Cole et al., 1992, Sadeh et al., 1994, Jean-Louis et al., 2001, Tryon, 2005, Kripke et al., 2010). As actigraphic devices have evolved, so too has the number of channels used to collect additional data streams (light, event markers, subjective scores, and off-wrist capacitance). (Ancoli-Israel et al, 2003)

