In conclusion, scientific research suggests that in the clinical setting, actigraphy is reliable for evaluating sleep patterns in patients with insomnia, for studying the effect of treatments designed to improve sleep, in the diagnosis of circadian rhythm disorders (including shift work), and in evaluating sleep in individuals who are less likely to tolerate PSG, such as inpatient psychiatric patients. While actigraphy has been used in research studies for many years, it is only recently that the methodological issues have been systematically addressed in clinical research and practice. With those issues addressed, the use of actigraphy is now being applied to clinical practice. (Ancoli-Israel et al, 2003).

STUDY OBJECTIVES

Primary Objective

To evaluate the effect of the Sleep Program on duration of admission in HDU (compared to controls) and sleep duration (Actigraphy data), in male psychiatric HDU inpatient participants.

Secondary objectives

1. Sleep quality - improvement in the Pittsburgh Sleep Quality Index
2. Sleep efficiency- percentage time in bed vs percentage time asleep
3. To test the engagement (tolerability and practicality) with a structured Stimulus Control Therapy Program
4. Impact on use of as needed (PRN) hypnotics
5. To describe the characteristic of sleep, activity and light exposure of patients in a high dependency psychiatric unit using wrist actigraphy.

Hypotheses

- We hypothesise that a structured stimulus control program for sleep will shorten duration of admission at psychiatric HDU.
- There will be an improvement in the sleep duration and efficiency
- There will be an improvement in the quality of sleep via a reduction of the self-rated Pittsburgh Sleep Quality Index score, measured at the beginning and end of the study.
- Participants in the Bright Light Study will engage in a structured stimulus control therapy program and it will be well-tolerated.

STUDY DESIGN

Design, Study Groups, Number of Participants

This is a pilot study for a complex intervention and we do not know the effect of variance. We seek to test our methodology, exterminate recruitment and retention rates, feasibility and finally, determine the sample size. We also seek to highlight any issues with acceptability, compliance, and delivery of our interventions.

Number of centres

Single-centre, at [name] Centre, male High Dependency (psychiatric) Unit

Duration

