Given the pilot study nature we will describe the sample, and the outcomes using but only use analytical techniques to estimate potential effects using difference of means within person measures in SPSS. The pilot study is unlikely to generate sufficient data points for bivariate or multivariate regression modelling.

DATA SECURITY, STORAGE AND ARCHIVING OF STUDY DOCUMENTS

Data Safety and Storage

There are two forms of data collected in pilot study: digital data, and physical data handwritten on paper forms.

Digital Data

Patient name, MRN and date of birth are linked to a Participant ID number. This is kept on an Excel spreadsheet, which is password protected on a single desktop issued by the Sydney Local Health District. The computer will be kept on-site only, in the secured, staff-only section of PMBC, which is accessible via swipe card only. The patient data spreadsheet can only be accessible within a Sydney LHD premises which has access to the SLHD intranet. Back-up copy of this spreadsheet is kept within the Sydney LHD ICT infrastructure.

De-identified digital data includes all data that are entered digitally, and are only identifiable through Participant ID. This includes any digitised data from physical forms, actigraphy data, aggregate length-of-stay data, and so on. Computers with access to these files that are password-protected and individualised for the investigator.

For security, a complete back-up of the data will be kept on a separate, secure Sydney LHD laptop, and is performed on a daily basis. Periodic data analysis files will also be backed-up and kept. Primary access to the Sydney LHD computing facilities will be through physical access onsite and through the intranet. Security will be enforced through restricted, swipe-card physical access, passwords and different levels will be assigned to groups and individuals.

Physical Data

Physical data includes the following; patient-completed self-assessment forms (PSQI, sleep diary, Visual scales), equipment check-in and check-out equipment logs. These are identifiable to patient with *only* the Participant ID.

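### Retention and usable actigraphy are needed for a stated aim of this pilot but are not outcomes, early terminators are left out of results, and the main objective and three of four hypotheses are worded as claims of effect

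*Protocol*

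**What the plan says.** The Administrative Information table of the protocol gives the primary purpose as "Pilot Study, Feasibility Study". The Study Design section spells this out: "We seek to test our methodology, exterminate recruitment and retention rates, feasibility and finally, determine the sample size", followed by "We also seek to highlight any issues with acceptability, compliance, and delivery of our interventions". The Background adds that the Program is piloted "in order to determine its effect, variance of effect and feasibility".

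The outcomes and objectives are set as follows.

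- **Primary outcome** (Administrative Information): "Actigraphic changes in sleep duration (Respironics Actigraphy data", and nothing else.
- **Secondary outcomes** (same table): eight lines, covering sleep quality, self-reported duration, HDU length of stay, PRN sedatives, sleep efficiency, engagement in the group, autonomy and satisfaction.
- **Primary Objective**: "To evaluate the effect of the Sleep Program on duration of admission in HDU (compared to controls) and sleep duration (Actigraphy data".
- **Hypotheses**: the first reads "We hypothesise that a structured stimulus control program for sleep will shorten duration of admission at psychiatric HDU". The second and third predict better sleep duration and efficiency and a lower PSQI score. The fourth concerns engagement and tolerability.

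The Early Termination section keeps the data of men who stop early for discussion only and leaves them out of results and statistical analyses. The Statistical Analysis Plan section limits the work to describing the sample and estimating possible effects as within-person mean differences, and adds: "The pilot study is unlikely to generate sufficient data points for bivariate or multivariate regression modelling". Allocation is nonrandomized, the trial is open label, and the target sample size is given as not applicable.

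**The concern.** A pilot earns its place by telling the sponsor whether a larger trial can be run and how large it must be. Here the quantities that answer this (how many men stay in the Program, how many nights of watch data can be used) are implied or stated aims but have no outcome. The rule on early terminators also removes the men on whom a retention rate depends. They include men who leave because they cannot tolerate the Program, because their mental state worsens, or because they feel their sleep is good enough.

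At the same time, the headline objective and most hypotheses promise an effect. Men admitted to an acute unit may sleep better as they recover, whatever the Program does. An improvement read against those hypotheses could therefore be mistaken for evidence that the Program works.

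**Working it through.** The protocol gives no sample size, power, effect size or SD, so there is no figure of its own to reproduce. The check is a comparison of sections, followed by arithmetic on scale.

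**Step 1. Stated aims against listed outcomes.**

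| Aim (Study Design) | Matching outcome line (Administrative Information) |
|---|---|
| Recruitment rate | none |
| Retention rate | none |
| Compliance | in part: engagement in the group; nothing on watch wear or usable nights |
| Acceptability | autonomy, satisfaction (secondary) |
| Sample size for a later trial | change in sleep duration (primary) |

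Outcomes that measure retention or usable actigraphy: 0 of 1 primary and 0 of 8 secondary lines.

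**Step 2. The early-termination rule.** Let E men enrol and D stop early. Retention is (E − D)/E. The reported set holds only E − D men, so retention within it is (E − D)/(E − D) = 100%, whatever D is. For illustration, with E = 26 and D = 8, true retention is 18/26 = 69%, while the reported set shows 18/18.

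**Step 3. Wording of effect.** Three of four hypotheses, and the Primary Objective, are about effect. A within-person mean change in an open-label study without randomization is the sum of any Program effect and any change that would have occurred anyway, and nothing in the design separates the two. The Primary Objective also asks for length of stay against controls. The comparator line names other HDU patients and previous admissions. A contrast with other patients is not a within-person difference, which is the only effect estimate that the analysis section describes.

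**Step 4. Scale.** From the Duration section: 4-6 places, about 6 months, taken as 26 weeks. Mean stay is not given; 2, 4 and 8 weeks are assumed, the shortest being the protocol's own minimum dose.

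N = places × 26 / stay. The extremes are 4 × 26/8 = 13 and 6 × 26/2 = 78.

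The half-width of the 95% interval for mean change, in SDs of the change, is t(0.975, N − 1)/√N. The Wilson 95% interval is for an assumed 70% retention.

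| Assumed stay | N (4 to 6 places) | Half-width, SDs of change | Interval for 70% retention |
|---|---|---|---|
| 2 weeks | 52 to 78 | 0.28 to 0.23 | 57-81% to 59-79% |
| 4 weeks | 26 to 39 | 0.40 to 0.32 | 51-84% to 54-82% |
| 8 weeks | 13 to 19 | 0.60 to 0.48 | 43-88% to 48-86% |

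With an assumed SD of change of 60-90 minutes, the half-width runs from about 0.23 × 60 = 14 minutes to 0.60 × 90 = 54 minutes. These intervals cover sampling error only, not recovery over time.

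**Step 5. What this does to sizing.** The Sample Size section says the pilot will supply the size needed for the actigraphic outcome. That takes the SD of change and the share r of enrolled men who give usable data, because m evaluable men require m/r enrolled. Taking retention as a stand-in for r, 70% gives m/0.70 = 1.43m. Over the interval at N = 26 the figure runs from m/0.84 = 1.19m to m/0.51 = 1.96m. With early terminators left out of the results, r would appear as 1 and no allowance would be made.

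**The case against.** The strongest reply is that this pilot has mixed aims and says so. The Background names effect and its variance alongside feasibility, and the Sample Size section ties the primary outcome to sizing. Measuring change in sleep duration to learn its SD is a proper task for a pilot. This stands, and it is why sleep duration should stay as the outcome used for sizing.

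Nor is feasibility absent. Engagement, autonomy and satisfaction are listed outcomes. Secondary objective 3 covers tolerability and practicality. The Participant Time Line schedules program usage and adverse events, and terminations must be documented. This also stands. The gap is confined to recruitment, retention and usable actigraphy, and to the exclusion rule.

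A reader might infer that the pilot will be declared a success or failure on its sleep result. The protocol does not say so. It sets no success rule, test or progression threshold, and its analysis section speaks only of estimating possible effects. Missing thresholds are not a finding either, since they could sit in a separate analysis plan that is not shown.

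A reader might also infer that feasibility rates would be known precisely while the effect would not. The table above does not bear that out: at 13 men, an assumed 70% retention is compatible with anything from 43% to 88%. The advantage of a retention rate is that it can be interpreted without a control group.

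Finally, a simple proportion still in the Program at two weeks would be a poor outcome. Participation ends at HDU discharge, so early discharge, the very benefit that the first hypothesis predicts, would count as failure.

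**Conclusion.** The point holds in this form: the protocol states a retention aim, gives it no outcome, and excludes from results the men who determine it. A separate analysis plan could add detail, but the outcome list and the exclusion are fixed in the protocol itself. The Primary Objective and the first three hypotheses claim more than the design can show, and this follows from the lack of randomization, blinding and a described control analysis, not from small numbers alone.

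The counts in Steps 1 and 3 and the identity in Step 2 rest on the protocol's text only. The figures in Steps 4 and 5 rest on assumed stays of 2-8 weeks, an assumed SD of 60-90 minutes and an assumed 70% retention. They show scale and carry no weight in the conclusion.

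This should be corrected before first enrolment. It is not a reason to stop the pilot.

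**What to change.** 1. In Administrative Information and Study Objectives, name three main feasibility outcomes, each with a 95% confidence interval over all enrolled men: (a) the proportion who stop the Program before two weeks for reasons other than HDU discharge, with discharge and stopping because sleep has improved counted separately; (b) the proportion of Program nights with usable actigraphy; (c) the proportion of offered sessions attended, as the measure of engagement in the group. Give the recruitment rate beside them as a plain count.
2. Amend Early Termination so that men who stop early count in these results.
3. Keep change in actigraphic sleep duration as the outcome whose mean and SD are estimated for sizing the next trial.
4. Reword the Primary Objective and the first three hypotheses as quantities to be estimated with a 95% confidence interval, with no claim of effect.

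The cost is wording and a little more tabulation from watches, equipment logs and program-usage records that are already planned. The sponsor gives up an efficacy headline.

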	Ward environmental initiatives
Stimulus Control Therapy	
 • Consistent wake time at 7am encouraged by ward staff • Beanbags: an alternate place to sit other than the bed
Sleep Psycho-education	
 • Visual cues regarding specific sleep hygiene strategies around patient room and ward area. • Reinforcement, encouragement and further psychoeducation provided by nursing staff
Increased light exposure (regulating circadian rhythm)	
 • Using available open spaces wherever possible enhanced with early morning Retimer™ blue-green light goggles for those with sleep-phase delay
Relaxation	
 • Calming music during wind down • Quiet space with dim lights and beanbags

Activity Groups

Each participant will be invited to participate in thrice-per-week, 30-minute workshops in the program, which aim to provide psychoeducation about sleep, debriefing and sleep-promotion related

activities. It is also aimed at increasing daytime activity and enforcing a regular circadian rhythm. This is conducted on a repeated weekly cycle as outlined below. These sessions will take place on the outdoor area of the HDU (the balcony) where possible such that participants will receive continuous daylight exposure during these sessions. Each session will take place in mid-morning to lunchtime.

Session 1

Session 1 are on Mondays. They are facilitated by a senior Occupational Therapist and a peer-support worker and is designed to instil a routine of activity (via a Cooking group). Initial consenting and program information will be provided to a patient who is commencing. As well, actigraph watch and sleep diary will be provided to the commencing participant, allowing for ongoing record and feedback of their sleep parameters throughout their time in the program. Qualitative feedback regarding sleep will be collected during these sessions.

Session 2

Second sessions are held on Wednesdays, on the balcony of the HDU. They are facilitated by two psychiatry registrars. Prior to the sessions, participants' actigraph watches are collected and sleep data analysed by the research assistant. A visual representation of sleep duration and activity for each patient will be printed prior to the session and given to the registrars, and printouts are identifiable only by participant IDs.

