These sessions are held as a mini picnic with healthy snacks. During these sessions, printouts will be discussed individually with participants, especially with respect to their self-evaluation in their Sleep Diaries. This aims to increase insight and empower the participants to take a proactive role in their management.

As a group, the registrars will give further psychoeducation about sleep, with a focus on sleep hygiene, and addressing specific stimuli which affect sleep.

Wednesday sessions are also repeated in a weekly cycle. Patients in their initial and final weeks of the program will be asked to complete the Pittsburgh Sleep Quality Index, modified to reflect the quality of sleep within one week.

Session 3

Session three are held on Fridays and are repeated on a weekly basis. It is split into two components. Firstly, the morning session is in the form of a breakfast barbeque – which is open to the entire ward to participate. Facilitators of sessions 1 and 2 are able to join. This session is an informal way for participants and clinicians to freely exchange ideas and feedback, as well as to reinforce sleep psychoeducation provided in earlier sessions.

Secondly, there will be a booster session on Friday evenings, which is self-directed by the participants and is optional. It entails participants making use of the ward measures made available to them – to enhance relaxation and stimulus control.

Summary table of sessions

Session	Day and time	Content	Measurement tools	
			Sleep diary	Actigraphy
1	Monday 11:30am – 12pm	
 • Cooking group • Preliminary psychoeducation • Program information and obtaining consent • Providing actigraph watch and diary for participant 	X	X
	Tuesday	Nil active intervention for Day 2 participants complete diary +/- nurse Day8 participants - maintain stimulus control and am light goggles	X	X
2	Wednesday (Pre- session)	
 • Collecting watches + analysing actigraphy 	X	X
	Wednesday 11:30am – 12pm	
 • Outdoor session with snacks • Psychoeducation about • Stimulus Control Therapy, Sleep Hygiene • Present sleep results • Administer PSQI and one-item Sleep Quality measure (start and terminating session only) 		
	Thursday		X	X
3	Friday AM	
 • Outdoors session with bacon and eggs 	X	X

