	Friday PM 9 - 9:30pm	
 • Booster session • Wind down with beanbags • Headphones provided for relaxing music • Reinforcing stimulus control therapy 	X	X

Participant Time Line

Time Frame for Activity	Screen	Program cycle		
		At recruitment	Weekly	At discharge
Initial screening in handovers by clinical staff	X			
Initial medical assessment for appropriateness	X			
Self-report measures		X	x	X
Sleep Diary			X	
Qualitative evaluation Questionnaire				X
Ward initiatives		X	X	
Retimer™ Light goggles			X	
Actigraphy data		X	X	
Sleep Program groups		x	X	
Psychoeducation about sleep hygiene		X	X	
Program usage		X	X	X
Adverse event monitoring		X	X	X

Study Procedure Risks

1. Skin damage due to photosensitivity
Some medications, notably Chlorpromazine, are known to increase the photosensitivity of the skin. The Program entails exposure to natural and low intensity artificial light, which may cause irritation and minor sunburns.
2. Headache from tightness or poor fit of light spectacles
The Retimer™ light goggle is made from rigid plastic and are not adjustable for size of head. Therefore, it is possible that participants may experience discomfort on the ridge of their nose, or sections of the skin around the auricle which makes contact with the goggle.
3. Discomfort from artificial light
The Retimer light goggle emits light in two different intensity settings, which is projected upwards towards the light. Whilst the light intensity is safe, it may still be a source of discomfort and annoyance to the patient.
4. Sleep disturbance
The Program is an evidence-based intervention aimed to reset and align the circadian rhythm to normal daylight hours. However, there is a risk that the integrated intervention does not improve sleep quality and quantity, or indeed, may worsen them.
5. Psychological harm: wearing a watch which constantly collects data might further enhance persecutory or paranoid ideations in the sub-population of participants who are experiencing psychotic symptoms. However, given the study requires informed consent, the likelihood of a paranoid patient consenting to participate is small.

Given the non-invasive, interactive and patient-driven nature of the intervention, it is expected that participants will have minimal risks in the following domains:

- disclosure of sensitive personal information
- exposure of illegal activity
- economic harm
- discrimination, stigma or other social harm
- devaluation or harassment

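### The watch is first issued in the session that starts the programme, so the primary within-person change in actigraphic sleep has no unexposed baseline night

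*Protocol*

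**What the plan says.** The Administrative Information table gives the primary outcome as "Actigraphic changes in sleep duration (Respironics Actigraphy data". The Statistical Analysis Plan section estimates effects by "difference of means within person measures in SPSS", so each participant's own early recording is the reference for his later one.

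Under Session 1 (Monday), "actigraph watch and sleep diary will be provided to the commencing participant". The same session is "designed to instil a routine of activity (via a Cooking group", and the Summary table of sessions lists "Preliminary psychoeducation" for it, together with consent and "Providing actigraph watch and diary for participant".

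The Participant Time Line marks actigraphy from recruitment onwards and not at screening. The recruitment column also carries the first marks for ward initiatives, programme groups and "Psychoeducation about sleep hygiene". The light goggles are marked only in the weekly column.

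Under Session 2 (Wednesday), "Patients in their initial and final weeks of the program will be asked to complete the Pittsburgh Sleep Quality Index". The summary table places that questionnaire and a one-item sleep quality rating in the session that teaches stimulus control and presents the actigraphy results. The appendix version of the questionnaire asks about the past week.

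**The concern.** A within-person change measures what a programme does only if the first measurement precedes the programme. Here the device that records the primary outcome is handed over in a session that already delivers two of the programme's named mechanisms, daytime activity and sleep education. No run-in or earlier recording is described.

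The comparators in the Administrative Information table concern length of stay and previous admissions, so they do not supply a sleep reference. Nights that were never recorded cannot be restored by any later analysis plan.

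The pilot's stated purpose includes determining the effect and its variance, and the Sample Size section says the pilot will determine the sample size for this outcome. The reference point of the change therefore affects the main product of the study.

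**Working it through.** The protocol states no effect size, standard deviation or sample size for this outcome, so there is no figure to reproduce. The check is a count of nights from the schedule.

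**Inputs (Protocol).** Session 1 is on Monday, 11:30am to 12pm, with watch issue, cooking group and introductory education. Session 2 is on Wednesday at the same hour, with watch data collected beforehand, then stimulus-control teaching, results and questionnaire. Questionnaire recall is one week.

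**Actigraphy.**
- Nights recorded before any programme content: 0, because the watch is issued in Session 1 and actigraphy has no screening mark.
- Nights recorded after Session 1 and before Session 2: Monday and Tuesday, so 2.
- Exposure on those 2 nights: Monday's content has been delivered and the ward initiatives may already have begun. Stimulus-control teaching is listed for Wednesday. The Tuesday row of the summary table records no active component for someone on his second day, whereas someone on day 8 continues stimulus control and goggles. Exposure is therefore low, but it is not shown to be nil.

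**First PSQI.** A one-week recall from Wednesday covers the nights of Wednesday, Thursday, Friday, Saturday, Sunday, Monday and Tuesday.
- Before Session 1: 5 of 7.
- After Session 1: 2 of 7, or 2/7 = 29%.

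**Effect on the estimate.** Let f be the fraction of the programme's effect on sleep duration already present on the first recorded nights. Taken alone, this contamination gives:

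measured change = (1 − f) × programme effect.

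The protocol gives no value for f. As an assumed range only, f = 0 leaves 100% of the effect and f = 0.5 leaves 50%. Given the low exposure on the first two nights, f near 0 cannot be ruled out.

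**The case against.** The best defence is that the first two nights come close to a baseline. Monday's content is a 30-minute group, stimulus-control teaching follows on Wednesday, and the goggles are not marked at recruitment. This stands as a limit on the size of the problem. It does not remove it: the protocol never designates those nights as baseline, and they follow Session 1.

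A reader might infer that the PSQI also lacks a pre-programme baseline. It does not, since about 5 of the 7 recalled nights precede Session 1.

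A reader might also infer that participants rate their sleep after seeing their own results, because the questionnaire is listed last for Wednesday. The bullets do not establish an order; Monday's list puts consent after the cooking group. What can be said is that nothing requires the rating to come first.

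The direction of bias also needs care. Early exposure by itself shrinks the apparent change. In an uncontrolled comparison during an acute admission, natural recovery could push the measured change the other way, and a clean baseline would not cure that.

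Finally, this is a pilot that claims only to estimate potential effects. That tempers the consequence. It does not excuse a reference point that costs little to move.

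**Conclusion.** The point holds for the primary actigraphic outcome. The schedule yields 0 unexposed nights and at most 2 lightly exposed ones before the Wednesday session, so the change compares early-programme with late-programme sleep. Early exposure would tend to understate any programme effect, and a sample size derived from an understated effect would be larger than needed. The amount cannot be computed from the protocol; the range for f shown above is an assumption.

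For the first PSQI and the one-item rating, both secondary, the baseline is partly contaminated (about 2 of 7 recalled nights for the PSQI) and is unprotected against feedback.

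It would go too far to say that the effect estimate, its variance and the future sample size are all wrong. No error in the variance follows from the documents, and the length-of-stay part of the primary objective is not affected. The count assumes that participants commence on a Monday, as Session 1 describes.

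**What to change.** 1. **Reconcile the consent timing.** Session 1 and the summary table put consent in the Monday session, while the Informed Consent Process gives up to a week to decide and allows the decision to be deferred further. Align these sections so that consent can be signed before a participant's first Monday session.
2. **Move the measurement.** At signed consent, issue the watch and diary and collect the first PSQI and visual analogue rating. Amend the Participant Time Line to match.
3. **Define the actigraphy baseline** as all nights recorded before first programme content. Where a participant has none, label his first two nights a partly exposed baseline and report him as such. The start of the programme is not delayed to gain nights. A minimum number of baseline nights is a matter of preference and does not follow from the protocol.
4. **Fix the order of self-report.** At the start and final Wednesday sessions, and at each weekly visual analogue rating, collect the rating before the printout is shown and before teaching. The PSQI stays a start-and-end measure.

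**Cost.** Four sections need consistent rewording, the watch is worn a few days longer, and the number of baseline nights will vary between participants. The Friday morning session is open to the whole ward and reinforces sleep education, so some exposure before enrolment may remain; it should be recorded where known.
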